6.2. National panel recruitment information

According to Qualtrics' IRB Information Sheet, "Participants are recruited from various sources, including website intercept recruitment, member referrals, targeted email lists, gaming sites, customer loyalty web portals, permission-based networks, and social media, etc." With regards to how panel members are invited to a survey, "Panel members are sent an email invitation or prompted on the respective survey platform to proceed with a given survey. The typical survey invitation is generally very simple and generic. It provides a hyperlink which will take the respondent to the survey as well as mention the incentive offered." More information is available in the Qualtrics' IRB Information Sheet attached under Section 3.0 of the "Miscellaneous Attachments" page in the IRB smartform system.

6.3. Informed consent process

The first page of the Qualtrics survey will display the information outlined in the informed consent form document. Specifically, the following passage will be included on this informed consent page, "Completion and return of the survey implies that you have read the information in this form and consent to take part in the research. Please keep this form for your records or future reference."

6.4. Timeline. The proposed pilot study is funded through the CTSI. As such, the study team is required to receive UF IRB approval prior to the procedures being submitted to NCATS for additional review. The additional review required by NCATS is expected to take two months. Thus, it is important for the study team to receive SRMC approval for the randomized message design experiment that was funded by the CTSI as soon as possible.

6.5. Stimuli. The speech of the VHA will be manipulated by varying its Dialect Density Measure (DDM) which is the number of dialectal features that are specific to AAE within an utterance in proportion to the number of words spoken in that given utterance. At the pronunciation level, this may include features such

as -g dropping, as in, "I'm gettin' a cold." At the grammatical level, this may include features such as the zero copula/auxiliary ("be" verb) as in, "How you feeling today?"

The scripts with different levels of dialectal density will be read by professional voice actors/actresses. Specific instructions and speech samples illustrating our target AAE features will be provided to the voice actors to ensure a natural and native production of AAE. The instructions will be designed by our team's linguists who have experience conducting linguistic fieldwork and communicating with laypeople without using technical terminologies.

AAE linguistic features to be added will be drawn from linguistic literature and scholarly research (as outlined in Section B.2.). Further, to ensure that each feature is an authentic representation of AAE, the [Corpus of Regional African American Language \(CORAAL\)](#) (Kendall & Farrington, 2020) will be consulted on the particular feature in question to ascertain whether the feature actually appears in the speech of various African Americans. CORAAL is a corpus of over 150 hours of recordings of interviews with African Americans from around the country and over time. CORAAL is especially beneficial in this process as it contains the speech of African Americans who differ in gender, age, and regionality, and the recordings span the late 1960s to the late 2010s. As much as possible, actual audio snippets of African American speakers using the linguistic feature in question will be included in the script via hyperlink both as an accountability mechanism to ensure the scripts avoid incorrect, stereotyped language and also to offer voice actors/actresses real life examples of the features to assist them in producing the most authentic and natural voice recording possible.

6.6. Measures. The primary outcome in the current pilot study is credibility score. We expect that source credibility is the mechanism through which intentions to screen will be strengthened. Source credibility will be measured using a series of semantic differential items (e.g., "Please rate your virtual health assistant on the following dimensions": Trustworthy/Untrustworthy, Honest/Dishonest, Expert/Inexpert, Competent/Incompetent). Further, we will measure whether the integration of AAE linguistic features impacted credibility through the use of usability questions (e.g., "How would you describe your virtual health assistant on the following scales:" "Is similar to me/Is different from me", "Speaks like me/Does not speak like me"). Given that the primary manipulation in this study is speech characteristics associated with ethnic group membership, we will also assess strength of ethnic identity using the Multi-group Ethnic Identity Measure.³⁹

6.7. Sample size justification and statistical analysis plan. As this is a pilot study, our main purpose is preliminary information collection and exploratory analysis instead of hypothesis testing, a formal sample size calculation is not necessary. The study sample size is determined by budget.

Descriptive statistics for credibility score including mean, standard deviation, median, and inter-quartile range (IQR) will be calculated (1) in the overall study cohort and (2) within each of the 7 groups. Similarly, descriptive statistics for intention to CRC screen including frequency and proportion will be calculated (1) in the overall study cohort and (2) within each of the 7 groups. Such information will serve as preliminary estimates to facilitate future powered studies. We will also generate descriptive statistics of collected demographic and clinical variables (e.g., age, gender, etc.). Graphical illustration will be provided if applicable. One-way ANOVA or Kruskal-Wallis test will be used to test difference of credibility score among 7 groups and two-sample t-test or Wilcoxon rank sum test will be used for post-hoc pairwise comparison. Chi-squared test or Fisher exact test will be used to test difference of intention to CRC screen among 7 groups and pairwise comparison. As this is a pilot study, all statistical analysis is exploratory. Therefore, multiple comparison adjustment will not be considered.

6.8. Patient-centeredness. The proposed intervention will test different levels of linguistic variation. To maximize patient centeredness, the investigators will conduct formative research with members of the intended patient population during the period in which the current study is under review at NCATS. The co-PI ([name]) currently has an open protocol in which focus groups are being used to ensure patient acceptability of all aspects of the VHAs. For more details on focus group procedures, please see our recent manuscript published in *Psycho-Oncology* (see [name] et al., 2020). [name] will conduct additional focus groups to examine patient perceptions of the different levels of linguistic variation and use this feedback to finalize how the stimuli are presented in the experiment to maximize patient centeredness.

5. Possible Discomforts and Risks:

- As with any behavioral intervention, there is the possibility of minimal emotional discomfort from being presented with individual risk factors for a disease. However, the probability of any physical, psychological, or social harm is minimal to none.

Adverse Event Reporting

- The data is collected by Qualtrics, so we will not have any direct contact with participants. The adverse event we will potentially encounter is someone sharing something concerning in the written feedback section. If this occurs, we will contact Qualtrics so they can reach out to the participant.

Data Sharing Plan

- We will share data associated with the trial by depositing these data in Dropbox, a file sharing system approved by UF Integrated Risk Management and providing access to the relevant files with outside investigators. Data include participant responses to survey questions and information about participant interactions with the intervention. Data are deidentified by Qualtrics and we do not have access to anything personally identifiable for participants.
- Data will be shared with investigators working at other accredited universities for the purposes of analysis. The names and Institutions of persons either given or denied access to the data, and the bases for such decisions, will be recorded. Participants will acquire IRB approval from their home institution to review data.

6. Possible Benefits:

- There are no direct benefits from participating in this study. However, participants may have garnered valuable information on their individual risk of developing colorectal cancer. They also learned how to screen for colorectal cancer.

7. Conflict of Interest:

- There are no real or potential conflicts of interest in regards to this research project for any members of the study team.

8. Bibliography

Aune, R. K., & Kikuchi, T. (1993). Effects of Language Intensity Similarity on Perceptions of Credibility Relational Attributions, and Persuasion. *Journal of Language and Social Psychology*, 12(3), 224–238.

Baugh, J. (2018). *Linguistics in pursuit of justice*. Cambridge University Press.

Bourhis, R. Y., & Giles, H. (1977). The language of intergroup distinctiveness. In H. Giles (Ed.), *Language, ethnicity and intergroup relations* (pp. 119–135). Academic Press.

Bourhis, R. Y., Roth, S., & MacQueen, G. (1989). Communication in the hospital setting: a survey of medical and everyday language use amongst patients, nurses and doctors. *Social science & medicine* (1982), 28(4), 339–346. [https://doi.org/10.1016/0277-9536\(89\)90035-x](https://doi.org/10.1016/0277-9536(89)90035-x)

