The speech of African Americans, then, is a mosaic, rather than a monolith. At the same time, however, Black linguists and scholars estimate that between 80-90% of the African American population retain and utilize a selection of the linguistic features of AAE at varying level as they weave through the various interactions in their lives (Smitherman, 1998; Rickford, 1999; Hutcheson, 2018). We find it plausible, therefore, that many of the participants in this study may utilize these features at some level as well and may find our VHA's linguistic accommodation appealing.

B.3. Linguistic accommodation. The connection between dialect density and cancer screening adherence has to do with trust and accommodation. Accommodating to a shared linguistic style improves communication effectiveness, understanding, and trust, which can lead to message compliance (Giles et al., 2007). Both objective and perceived language similarities enhance perception of credibility, competence, and persuasiveness (Aune & Kikuchi, 1993). In the clinical setting, healthcare providers who

¹ The term African American Vernacular English (AAVE), among others, has also widely been used.

² African American English is also not limited to the African American community but can be the first language of any person.

match their communication style to that of patients are considered most appropriate (Bourhis, Roth, & MacQueen, 1988). This is especially salient among racial ethnic minorities, who may maintain or accentuate linguistic features tied to racial identity in order to protect their racial identity (Bourhis & Giles, 1977, Giles & Johnson, 1987). For example, racial minorities might view “standard” language as more socially desirable but find the “non-standard” similar accent persuasive (Giles, 1973). Therefore, making an African American healthcare provider option with shared linguistic features is not cultural insensitivity, but rather a potential accommodation to those whose speech patterns also have non-standard linguistic features.

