Interventions that use tailored messages are effective for improving CRC screening. However, two important questions must be answered before tailored screening interventions can be implemented in healthcare systems. One is the degree to which message content must be tailored to be effective and another is how to effectively engage participants. The current project is an extension of an existing project that uses mobile virtual human technology (VHT) to deliver tailored CRC screening messages for African Americans to improve screening within guidelines. Interventions using VHT offer numerous advantages, including the capability to be customized to the linguistic preferences of the patient. As such, the use of virtual technology could help reduce CRC screening barriers such as cultural mismatch and low self-efficacy among African American patients.

The purpose of this proposal is to investigate to what extent the incorporation of AAE linguistic features increases, decreases, or has no effect on the perceived credibility of VHAs. This pilot study is meant to be exploratory in nature. We seek to explore the following specific aim:

- Examine how tailoring the dialectal variety of the speech of VHAs influences their perceived credibility. **Approach:** Each participant will interact with a VHA that differs in speech containing

either: (1) strictly linguistic features of SAE, (2) a low level integration of AAE linguistic features, (3) a high level integration of AAE linguistic features, or (4) a voiceless, text-only control. Post-interaction, participants will be asked to judge how credible they felt the VHA was through survey questions.

4. Research Plan:

6.1. Pilot study design. This pilot study will use a posttest-only, 3 (SAE: Standardized American English / low level AAE: African American English / high level AAE) x 2 (Introduction / No introduction) with a control group (i.e., no voice) randomized experimental message design. Patients (N=750) will be recruited from a national panel by Qualtrics. In order to be included in the study, participants must be between the ages of 45-75, and have health insurance. We will recruit equal numbers of male and female patients.

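### Does analysing credibility as one score, with no separate trust and expertise results, undermine the pilot's answer?

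*Combined protocol and SAP*

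**What the plan says.** Section 6.6 (Measures) makes one score the primary outcome: "The primary outcome in the current pilot study is credibility score". On the instrument it says "Source credibility will be measured using a series of semantic differential items", and it gives four item pairs as examples: "Trustworthy/Untrustworthy, Honest/Dishonest, Expert/Inexpert, Competent/Incompetent". It states neither the number of items, nor the response range, nor how items combine into a score, and it names no subscales.

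Section 6.7 plans the mean, SD, median and IQR of that score, overall and in each of the 7 groups. It then says "One-way ANOVA or Kruskal-Wallis test will be used to test difference of credibility score among 7 groups", followed by pairwise t-tests or Wilcoxon tests. All analysis is labelled exploratory and no multiplicity adjustment is made. On the use of the descriptive results it says "Such information will serve as preliminary estimates to facilitate future powered studies".

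The aim in section 3 is open on direction. It asks to what extent adding "AAE linguistic features increases, decreases, or has no effect on the perceived credibility of VHAs". Background B.3 says "Both objective and perceived language similarities enhance perception of credibility, competence, and persuasiveness". It also notes that minority listeners may rate standard speech as more socially desirable and yet be persuaded by a non-standard accent similar to their own.

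**The concern.** Two of the example items (trustworthy, honest) concern trust, and two (expert, competent) concern expertise. Dialect could plausibly affect these differently: a voice closer to the listener's own might gain trust without gaining, or while losing, perceived expertise. If so, averaging the items shrinks the effect, and equal and opposite shifts vanish.

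Two things would be at stake. First, the aim allows an answer of no effect, and a null single score cannot separate three cases: neither dimension moved, only one moved, or the two offset each other. Second, the pilot is meant to supply estimates for later powered studies, and the planned tables would carry no mean or SD by dimension.

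**Working it through.** The plan gives no power figure to reproduce; section 6.7 says the sample size was set by budget.

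**Inputs from the documents.** N = 750 (section 6.1) and 7 groups (section 6.7).

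**Assumptions, none of them in the documents.** Equal allocation; exactly two dimensions, each with SD 1 and equal weight; trust-expertise correlation r of 0.3, 0.5 or 0.7; trust effect t = 0.3 SD; two-sided 0.05; one pairwise t-test.

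**Group size.** 750/7 = 107.1 per group.

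**Trust subscale alone.** d = 0.3. The noncentral t with 2n − 2 degrees of freedom gives 59% power. The 95% CI half-width is 1.97 × √(2/107.1) = 0.27 SD.

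**Single score.** With an expertise effect e, the mean shift is (t + e)/2 and the SD is √((1 + r)/2), so d = [(t + e)/2] / √((1 + r)/2). For e = 0 and r = 0.5 this is 0.15/0.866 = 0.173.

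| Expertise effect e | d at r = 0.3 / 0.5 / 0.7 | Power on the single score |
|---|---|---|
| +0.30 | 0.372 / 0.346 / 0.325 | 77 / 71 / 66% |
| +0.15 | 0.279 / 0.260 / 0.244 | 53 / 47 / 43% |
| 0 | 0.186 / 0.173 / 0.163 | 27 / 24 / 22% |
| −0.15 | 0.093 / 0.087 / 0.081 | 10 / 10 / 9% |
| −0.30 | 0 / 0 / 0 | 5% (alpha only) |

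**Break-even.** The single score beats the trust subscale when e/t exceeds 2√((1 + r)/2) − 1, which is 0.61, 0.73 and 0.84 for r = 0.3, 0.5 and 0.7. So the score may be much worse or clearly better than a subscale, and nothing in the documents fixes e/t.

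**Do the documents predict divergence?** The B.3 sentence that names one of the example dimensions puts competence alongside credibility and persuasiveness, all rising with language similarity. The other B.3 statement contrasts social desirability with persuasion. Neither is trust or expertise, and persuasiveness is not among the example items. Divergence is possible but not predicted.

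**Would separate subscale tests settle it?** Only in part. Finding one subscale significant and the other not does not show that they moved differently. That needs the between-group contrast in trust minus expertise, whose half-width is 0.27 × √(2(1 − r)): 0.32 SD at r = 0.3 and 0.21 SD at r = 0.7. Testing both subscales pairwise would add 2 × (7 × 6/2) = 42 unadjusted comparisons, with 42 × 0.05 = 2.1 expected below 0.05 by chance if nothing differs.

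**The case for a change.** The best case for a change is that it is cheap and fits the pilot's stated purposes. The items are already collected, so subscale summaries add two rows per table. With no multiplicity adjustment in the plan, they take no alpha from the primary outcome. Means and SDs by dimension would help size a later study, and fixing the item grouping beforehand removes a choice otherwise made after seeing the data. The lack of a scoring rule also means the text alone does not let a reader compute the primary outcome.

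Much of this stands. Section 6.6 does not define the score, and the dilution is real if the effect is confined to one dimension. But these points support an optional addition and do not show a fault in the analysis. The four items are examples only. The full questionnaire is not in these documents, so its length, its balance and any trust/expertise structure are unknown. The section 5 data sharing plan covers participants' survey responses, and section 6.7 labels everything exploratory. Dimension-level means and SDs can therefore be produced later without departing from the plan.

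**Conclusion.** No change is needed. The abstract's main question, the aim in section 3 and the mechanism in section 6.6 all refer to credibility as one construct, and a single score matches that. Followed as written, the plan gives a sound answer about overall credibility.

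The possible loss is conditional: 59% power falls to 22-27% if a 0.3 SD effect touches trust alone, and to 5% if expertise falls by the same amount. The possible gain is conditional too: 66-77% if both rise by 0.3 SD. These figures rest on equal allocation, two equally weighted dimensions and correlations of 0.3 to 0.7, all assumed. They describe a fair trade-off between one summary and two narrower ones. They are also power figures for a study that says it is collecting preliminary information and not testing hypotheses.

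What remains is the unwritten scoring rule, a gap that analysts would ordinarily fill by averaging or summing the rated items. Subscale summaries are a reasonable extra if the full item list supports them. Anyone who wants to claim divergence would need the trust-minus-expertise contrast (half-width about 0.21-0.32 SD), because separate subscale tests would not establish it.

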**University of Florida IRB-01
Protocol**

Title: A sociolinguistic-enabled web application to develop precision health intervention for African Americans

Investigators: [name] (PI), [name], [name], [name], , [name], [name], [name]

1. Abstract:

This pilot study will explore the preliminary efficacy of a colorectal cancer (CRC) screening intervention delivered by virtual health assistants (VHAs). Participants will include 750 patients in the US between the ages of 45 and 75 recruited through Qualtrics panels: 375 who are non-adherent to CRC screening guidelines, and 375 patients who are adherent to CRC screening guidelines. The main research question is: How does the integration of different levels of dialect density of the linguistic features of African American English (AAE) influence the perceived credibility of a Black VHA? Four types of VHAs will be presented to our patients: a VHA with Standardized American English (SAE) linguistic features, a VHA with a low level of African American English (AAE) linguistic features integrated, a VHA with a high level of African American English (AAE) linguistic features integrated, and a text-only control condition. Survey questions will be used to obtain credibility judgments about VHAs post-interaction.

2. Background:

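### The sample is fixed at 375 adherent and 375 non-adherent patients, but section 6.7 reports no outcome by adherence, so its tables cannot show whether the planning estimates depend on that mix

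*Combined protocol and SAP*

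**What the plan says.** The Abstract sets the composition of the 750 participants: "375 who are non-adherent to CRC screening guidelines, and 375 patients who are adherent to CRC screening guidelines". Section 6.1 repeats the total and asks for equal numbers of men and women, but its eligibility sentence leaves adherence out: "In order to be included in the study, participants must be between the ages of 45-75, and have health insurance".

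Section 6.7 plans summaries of credibility for the whole cohort and for each arm. Intention is handled in the same way: "frequency and proportion will be calculated (1) in the overall study cohort and (2) within each of the 7 groups". The tests follow the same structure. For credibility, "One-way ANOVA or Kruskal-Wallis test will be used to test difference of credibility score among 7 groups", with pairwise follow-up. For intention, "Chi-squared test or Fisher exact test will be used to test difference of intention to CRC screen among 7 groups and pairwise comparison". Adherence appears in no outcome table, test or model. The nearest text is a general line on describing demographic and clinical variables. That line could include adherence as a baseline count, but it does not cross adherence with an outcome.

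The same section states what the summaries are for: "Such information will serve as preliminary estimates to facilitate future powered studies".

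**The concern.** An overall mean or proportion from a sample fixed at 50:50 is a weighted average of two strata, and the recruiter chose the weights. It carries over to another population only if the outcome does not differ by adherence, or if the strata are reported separately so that they can be reweighted. The planned tables allow neither check.

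A different mix in a later study is realistic on the protocol's own account. Section 3 says adherence is low, particularly among African Americans, and that the wider project aims to improve screening. A later trial could therefore enrol mainly non-adherent people. At stake is how usable the planning figures are, not the validity of the comparisons between arms.

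**Working it through.** **Inputs from the documents.** 375 + 375 = 750 participants (Abstract; total repeated in 6.1). Arms: 3 × 2 + 1 = 7 (6.1). Both agree with the text. There is no power calculation to reproduce, because 6.7 says the sample size is set by budget.

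**Assumptions.** Equal allocation, which is not stated: 750/7 = 107.1 per arm and 375/7 = 53.6 per arm and stratum. A yes/no intention item. All rates, gaps and effects below, since the documents give none.

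**1. How far the pooled intention rate moves.** Pooled rate = w × p(adherent) + (1 − w) × p(non-adherent), where w is the adherent share.

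| Adherent / non-adherent rate | w = 0.3 | w = 0.5 | w = 0.7 |
|---|---|---|---|
| 60% / 40% | 46% | 50% | 54% |
| 50% / 40% | 43% | 45% | 47% |
| equal | no change | no change | no change |

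**2. What a table by adherence would show** (95% half-widths; proportions at 0.4 or 0.6, so p(1 − p) = 0.24).

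| Unit | n | Proportion: 1.96√(0.24/n) | Mean: 1.96/√n |
|---|---|---|---|
| Stratum | 375 | ±5.0 points | ±0.10 SD |
| Arm | 107.1 | ±9.3 points | ±0.19 SD |
| Arm within stratum | 53.6 | ±13.1 points | ±0.27 SD |

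For the gap between strata: 1.96√(2 × 0.24/375) = ±7.0 points, and 1.96√(2/375) = ±0.14 SD. A 20-point gap would be plain.

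**3. If the dialect effect itself differs by stratum.** Suppose dialect shifts credibility by 0.4 SD in non-adherent patients and by 0 in adherent patients. The pooled effect is (0.4 + 0)/2 = 0.2 SD. At 80% power and two-sided 5%, n per arm = 2 × (1.960 + 0.842)²/d². This gives 393 for d = 0.2, against 99 for a trial in non-adherent patients alone. If the effect is 0.4 SD in both strata, the answer is 99 either way.

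**4. What adjusting the tests for adherence would gain** (two arms of about 107, two-sided 5%).

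Intention: pooled two-proportion test against a Cochran-Mantel-Haenszel test, both by normal approximation.

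| Non-adherent arms; adherent arms | Pooled | Stratified |
|---|---|---|
| 40 vs 60%; 40 vs 60% | 83.8% | 83.8% |
| 40 vs 60%; 50 vs 70% | 84.2% | 84.6% |
| 40 vs 50%; 60 vs 70% | 31.2% | 32.3% |
| 40 vs 60%; 60 vs 80% | 85.3% | 86.8% |
| 40 vs 60%; 80 vs 90% | 65.1% | 71.8% |
| 40 vs 60%; 90 vs 90% | 35.8% | 42.6% |

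Credibility: leaving out a gap of g SD between strata inflates the SD by √(1 + g²/4), which is 1.005 at g = 0.2 and 1.031 at g = 0.5. Power for a 0.4 SD arm difference is then 82.6% and 80.7%, against 83.0% adjusted.

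The gain is at most 1.5 points for intention at baseline gaps up to 20 points, and about 2 points for credibility at a 0.5 SD gap. About 7 points appears only at intention gaps of 40 to 50 points.

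**The case against.** The case for leaving the plan alone has several parts.

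- **No stated aim goes unanswered.** The research question is about dialect and credibility, and adherence is not named as a factor or moderator. Section 6.7 describes a pilot in which "our main purpose is preliminary information collection and exploratory analysis instead of hypothesis testing". This stands, and it keeps the severity low. It does not dispose of the point, because planning estimates are the stated use of these very tables.
- **The shift may hardly alter a later sample size.** Take a later trial seeking a 10-point rise at 80% power and two-sided 5%. The unpooled formula n = 7.849 × [p(1 − p) + (p + 0.1)(0.9 − p)]/0.01 gives about 388, 385 and 376 per arm at 46%, 50% and 54%, a range of about 3%. This is correct for moderate gaps. No passage supports a larger gap, and none says adherence predicts credibility.
- **The table could not settle the case with the largest consequence.** The half-width for a difference in effect between strata is 1.96√(4/53.6) = about 0.54 SD, so even 0.4 against 0 SD could not be reliably separated for a single pairwise contrast. This stands, and the arm-by-stratum table must be read as descriptive only.
- **Adherence is not the only fixed feature.** Sex is also balanced, and outcomes are not tabulated by sex. The 50:50 adherence mix is at least disclosed in the Abstract. That is fair, but disclosing the mix does not let a reader reweight to another one.
- **Others could re-analyse.** The Data Sharing Plan says: "Data will be shared with investigators working at other accredited universities for the purposes of analysis". This helps only if adherence is in the shared file and access is granted.

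**Conclusion.** The point holds as a low-severity improvement. The plan fixes the adherence mix and then reports nothing that shows whether its planning figures depend on it. The randomised comparisons are unaffected, and no figure in the plan is wrong.

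The size cannot be known from the documents. It runs from nothing, if the strata are alike, to a 4-point shift in overall intention under an assumed 20-point gap and a 30% or 70% adherent share. It would be larger if the dialect effect differed by adherence, but this study is too small to establish that. The main benefit is in reporting; the gain in precision from adjustment is secondary. Figures per arm rest on equal allocation.

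**What to change.** In section 6.7:

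1. Report credibility and intention within each adherence stratum (n = 375) with 95% confidence intervals. Add an arm-by-stratum table marked descriptive, and state that pooled planning figures apply to a 50:50 adherence mix. If only one change is made, it should be this one.
2. Optionally, include adherence as a factor in the credibility ANOVA and pairwise comparisons, or use a stratified rank test (van Elteren for pairs) on the nonparametric route. For intention, use a Cochran-Mantel-Haenszel test stratified by adherence, in its generalised form if the item has more than two categories.
3. Label any dialect-by-adherence term exploratory.

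It would also help to repeat the 375/375 split in 6.1.

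The cost is a few lines of text, one extra table and slightly more analysis. No participants are added, and the trial must already know adherence status to fill the two halves. The drawback is that cells of about 54 are imprecise, so they should not replace the arm-level figures as planning inputs.
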